1.0 Background and Rationale

1.1 Introduction:

According to the USDA Economic Research Service Food Availability Data, beef consumption has been on a general decline for the past 40 years, with current per capita consumption approximately 35% lower in 2020 than in 1980. Some of this decline over the past few years can be attributed to politically motivated claims that carbon emissions from cattle represent a major threat to the global environment. However, the major reason for declining beef consumption is the widely promulgated claim that beef is unhealthy. The hamburger in particular has become a poster child for the notion that beef consumption is responsible for the increasing occurrence of obesity in the United States. The trend of decreasing beef consumption due to perceived health concerns, particularly obesity and associated health problems, has led major fast-food chains such as Burger King and McDonalds, to offer vegetarian burgers as healthy alternatives to the traditional beef burger. However, examination

of the components of the macronutrient matrix of a typical vegetarian burger gives reason to question the health benefits as compared to a traditional beef patty-hamburger.

1.2 Previous research on the topic:

[figure not shown]
One of the principal nutritional benefits of dietary protein in a food source is the stimulation of muscle protein turnover and the net gain of body protein (the anabolic response) (1).

Table 1 shows key aspects of the macronutrient matrix of the Impossible Burger and an 80/20 percent beef patty, with particular emphasis on the protein/essential amino acid (EAA) content.

Table 1. Proposed Experimental Groups			
	80/20 Beef Patty	Impossible Burger	2 Impossible Burgers
Amount (oz)	4 oz	4 oz	8 oz
Protein (g)	19 g	19 g	38 g
EAA (g)	8.9 g	4.2 g	8.4 g
Calories	287	240	480
Calories / g EAA	32	57	57

The Impossible Burger was chosen as a representative vegetarian burger because soy, which is the highest quality plant-based protein, is the principal protein source (2). Four-ounce servings of a beef patty and of an Impossible Burger each provide 19 g of protein. However, a closer inspection of the macronutrient matrix of the two food sources reveals that the 4 oz beef patty contains more than twice the amount of essential amino acids (EAAs) as compared to a 4 oz Impossible Burger. We recently completed an NCBA-supported study in which the anabolic responses to seven different “ounce equivalents” of protein food sources, as described by the USDA My Plate, were quantified using stable isotope tracers. Rather than being metabolically equivalent, as implied by their designation by My Plate as “ounce equivalent” protein food sources, we found that there was a linear relation between the net gain in body protein and the EAA content of the protein food source (**Figure 1A**) (3). Moreover, the slope of the relation between EAA content and increase in net protein balance was approximately 1, meaning that any difference in EAA content directly corresponded to an equivalent difference in net body protein gain (**Figure 1B**).

These results support the notion that the EAA content of a protein food source is principally responsible for the magnitude of the anabolic response. This fundamental concept is the basis for the scoring of protein quality by the Digestible Indispensable Amino Acid Score (DIAAS) (4). With relevance to the comparison of a beef patty and an Impossible Burger, we found that consumption of 2 ounces of beef resulted in an anabolic response that was approximately 4 g net gain of protein greater than the response to consumption of 2 ounces tofu (Figure 1) (3). The difference in anabolic responses corresponds to the difference in the EAA content of the two protein food sources (Figure 1A). Muscle protein fractional synthesis rate was also greater in those consuming beef as opposed to tofu. Further, compilation of our in-house data set across various populations and food sources indicates that the EAA content of a protein food source explains 80.4% of the variance in the total amount of body protein gained (5). This

large dataset has allowed us to develop a predictive equation that indicates the total amount of body protein gained will be 7.6 g from 4.2 g of EAA (the Impossible Burger) and 16.5 g from 8.9 g of EAA (beef patty). Stated differently, the greater EAA content of a 4 oz beef patty is predicted to elicit more than double the anabolic response to the same amount of an Impossible Burger.

Plant-based burgers such as the Impossible Burger are being marketed as a one-for-one replacement for beef-based burgers, but the disregard for protein quality is misleading and creates a false perception of equivalent nutritional benefit of the two protein food sources. In

addition to the greater EAA content per gram protein, the profile of EAAs in beef protein more closely reflects the dietary requirements for individual EAAs, as reflected by a DIAAS approximately 40% greater than soy protein. In addition, the overall macronutrient matrix of a protein food source can potentially influence the anabolic response by affecting the temporal EAA response. Both the peak concentration of EAAs after consumption as well as the time to reach the peak concentration affect the anabolic response (5). The Impossible Burger contains various binders and starches that could potentially interfere with the absorption of the EAA from the protein matrix, with a resultant slowing of the rate of absorption and blunting of the maximal concentrations of EAAs in the blood and the speed at which the peak concentrations are reached. These factors likely have a corresponding negative impact on the magnitude of the anabolic response. Since no such issues impede the digestibility of beef protein, it is reasonable to propose that the plasma EAA levels will reach higher peak EAA concentrations, and achieve the peak concentrations more rapidly, than ingestion of the same amount of EAAs in the matrix of the Impossible Burger. As a result of both the advantageous profile of EAAs in beef protein and the more rapid absorption of EAAs, we propose that a beef patty will not only provide a greater anabolic response than an iso-nitrogenous amount of Impossible Burger, but that also consumption of 4 oz of beef patty will also elicit a greater anabolic response than consumption of two Impossible Burgers.

The caloric value of the Impossible Burger and a beef patty is also relevant when considering the relative nutritional value and nutrient density of the two protein food sources. The caloric value of the Impossible Burger is almost twice that of a beef patty when normalized for the amount of EAAs (Table 1). We therefore anticipate that differences in anabolic responses between a beef patty and Impossible Burger will be amplified when normalized by the caloric values of the two protein food sources.

2.0 Hypotheses

1. Consumption of a 4 oz beef patty will result in a greater anabolic response than consumption of a 4 oz Impossible Burger, including greater increases in plasma EAA

concentrations, a greater balance between whole body protein synthesis and breakdown, and a greater increase in muscle protein fractional synthetic rate (FSR).

2. Consumption of a 4 oz beef patty will result in a greater anabolic response than consumption of two 4 oz Impossible Burgers, including greater increases in plasma EAA concentrations, greater balance between whole body protein synthesis and breakdown, and greater increase in muscle protein FSR.

3.0 Study Design and Procedures

We will enroll up to 28 subjects with a goal to study up to 24 healthy male and females. We will use a 10-hour period to measure the protein metabolism in response to the study food (one beef patty, one vegi-burger, or two vegi-burgers).

3.1 Study Visits

Visit 1: subjects will come to the UAMS TRI for informed consent discussion. Once consent is obtained, subsequent study procedures will be performed. A medical history questionnaire including allergies and list of current medications will be completed. Females of child bearing capacity will be asked to provide a urine sample for pregnancy testing. About 4mL of venous blood will be drawn to send for complete blood count for study criteria. Blood and urine samples will be sent to LabCorp.

Subjects will be asked to perform the following tests and measurements at visit 1:

Standing height without shoes (in cm),

Body weight without shoes (in kg),

If subject meets the requirements (fasted for at least 8 hours, caffeine-free for at least 12 hours, and did not perform strenuous exercise during the past 24 hours) to perform the DEXA scan and In Body scan on visit 1, these tests will be performed at that time. If they do not, these tests will be performed at Visit 2.

Run-in meals will be discussed with subjects to elicit food allergies or intolerances.

Visit 2: Subjects return to the UAMS TRI. If they will undergo the DEXA and InBody scans, the must have fasted for at least 8 hours, avoided caffeine for at least 12 hours, and avoided strenuous exercise during the past 24 hours. They will be asked about any adverse events since last visit. The In Body, DEXA, ultrasound scans will be performed if these were not done at visit 1. Two days' of run-in meals will be dispensed with instructions on their preparation. Meals will be consumed for the two days immediately preceding Visit 3.

Visit 3: Subjects return to the UAMS TRI having fasted overnight. Study staff will ask about adverse events since their last visit. Vital signs (heartrate, blood pressure and oral temperature) will be measured. The study nurse will insert an IV catheter into a vein of one of the subjects' arms to use for periodic blood sampling, warming the arm by means of a heating pad or a heated plastic box. A second IV catheter will be placed into a vein on of the subject's other arm to use for stable isotope infusion.

After an initial blood sample is obtained, the priming dose of isotopes are given IV push, the constant infusions are begun, and a timer is started. Blood and muscle samples are obtained according to the schedule below.

The study food is served after the 4:00 blood/muscle sample are obtained. Subjects are asked to consume the study food within 10 minutes.

At the conclusion of 10 hours elapsed time, the IV catheters are removed and the sites dressed with a bandage. Vital signs (heartrate, blood pressure and oral temperature) will be measured. A snack and beverage will be offered to the subject. Subject will then be free to leave.

Elapsed time (min., approximate)	Procedure
-0	Blood sample (~4mL into an EDTA tube)
120	Blood sample (~4mL into an EDTA tube), ingest study supplement, muscle sample from vastus lateralis
150	Blood sample (~4mL into an EDTA tube)
180	Blood sample (~4mL into an EDTA tube)

210	Blood sample (~4mL into an EDTA tube)
240	Blood sample (~4mL into an EDTA tube), muscle sample from vastus lateralis serve study food
270	Blood sample (~4mL into an EDTA tube)
300	Blood sample (~4mL into an EDTA tube)
330	Blood sample (~4mL into an EDTA tube)
360	Blood sample (~4mL into an EDTA tube)
390	Blood sample (~4mL into an EDTA tube)
420	Blood sample (~4mL into an EDTA tube)
450	Blood sample (~4mL into an EDTA tube)
480	Blood sample (~4mL into an EDTA tube)
510	Blood sample (~4mL into an EDTA tube)
540	Blood sample (~4mL into an EDTA tube)
570	Blood sample (~4mL into an EDTA tube)
600	Blood sample (~4mL into an EDTA tube), muscle sample from vastus lateralis

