3.3 Recruitment

Potential subjects will be recruited from the Little Rock and central Arkansas areas by use of UAMSHealth social media, word of mouth, the ARResearch.org registry, and contacting prior subjects who indicated they wanted to be contacted about future studies. UAMS students and employees will not be targeted for participation but will not be refused. Study staff will ask enrolled subjects to recruit others if they are comfortable doing so, and study staff will seek subjects within their social circles. Individuals interested in the study will be scheduled for Visit 1.

Facebook Script:

The Center for Translational Research in Aging and Longevity at UAMS is recruiting healthy individuals ages 18-40 for a study about measuring how blood and muscle proteins respond to either a beef patty or vegi-burger(s).

Participants will be compensated for their time. If interested, please contact us:
Email [contact] or call [contact] for more information.

Twitter Script:

Our research team is recruiting individuals ages 18-40 for a study about how blood and muscle proteins respond to a beef patty vs vegi-burger.

Participants will be compensated! Contact us for more info: email [contact], or call [contact]

During the initial conversation (in person or via phone), the following items will be discussed in non-technical language:

- this study is completely voluntary.
- the goal of the study: to see if beef or vege-burgers are more efficient at making proteins in our body.
- the number of visits to UAMS study site and their duration: 2 visits that are less than an hour, and 1 visit that lasts a bit over 10 hours.
- study procedures: must have 2 IV catheters placed and undergo 3 muscle biopsies from one incision on their outer thigh, eat our food for almost 3 full days, fast overnight twice,

have an x-ray for body composition, must get an infusion of stable isotopes (and define what they are).

- risks of procedures: pain, bruising, bleeding, infection, possible fever/chills, discomfort from fasting, small amount of radiation from x-ray, amount of blood taken (approx.. 5 tablespoons), skin numbness and scar formation from biopsy incision.
- compensation for time and travel: up to \$340 if all 3 visits are completed.

ARRResearch.org:

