4.2 Exclusion Criteria

- Unwilling to eat animal proteins
- History of diabetes that requires medication for control of blood glucose

- History of malignancy or chemo/radiation therapy in the 6 months prior to enrollment
- History of gastrointestinal bypass/reduction surgery (Lapband, gastric sleeve, etc.)
- Pregnant females
- Hemoglobin less than 12 g/dL at screening
- Platelets less than 150,000 at screening
- Subjects who cannot refrain from using protein or amino acid supplements for 7 days prior to Visit 3
- Concomitant use of oral or injectable corticosteroids
- Concomitant use of testosterone, IGF-1, or similar anabolic agent
- Any other disease or condition that would place the subject at increased risk of harm if they were to participate, at the discretion of the study physician

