5.0 Risks and Benefits

There are no direct benefits for the subjects. Expected risks associated with this protocol are described in detail below. All experimental procedures will be performed by appropriately trained and credentialed personnel.

5.1 Blood sampling:

Blood samples will be collected solely for the purpose of experimentation. The blood will be used to measure plasma amino acid concentrations, stable isotope enrichment, glucose, and insulin. The total amount of blood taken will be approximately 72 mL (~5 tablespoons).

Subjects should have no noticeable effects from this volume.

5.2 DEXA, In Body, ultrasound scans:

The DEXA scan exposes subjects to approximately ½ of the radiation of one chest x-ray.

Subjects will undergo 1 DEXA scan. The In Body and ultrasound scans do not pose any risks.

5.3 Study foods:

The run-in meals are comprised of frozen, ready-to-eat portions that are commercially available at most grocery stores (e.g. Stouffers). The 'test' foods are:

- one 4 ounce (cooked weight) patty of 80/20 beef (from Kroger e.g.)
- one 4 ounce Impossible Burger (<https://impossiblefoods.com/products/burger>)
- two 4 ounce Impossible Burgers

The risk of eating any of these foods is that of a food allergy. Subjects will be shown the list of foods and asked if any of them are intolerable.

5.4 Stable Isotope Infusion:

The primary risks of infusion of the stable isotopes are fever, chills, infection (from contamination). A 0.2 micron in-line filter will be used during the infusion. The isotopes will be purchased from Cambridge Isotope Laboratories (Tewksbury, MA, USA) and sent to the Center for Translational Research in Aging and Longevity at Texas A&M University (College Station, TX) for contractual compounding. Finished products will be shipped to the UAMS Research pharmacist who will store and dispense the isotopes to study staff as needed. Isotopes will be stored in glass vials and frozen until use. Two solutions will be produced: a mixture of L-[ring-²H₅] phenylalanine + U-¹³C₉-¹⁵N tyrosine (for constant infusion IVPB), and a mixture of L-[ring-²H₅] phenylalanine + U-¹³C₉-¹⁵N tyrosine + L-[ring-²H₄] tyrosine (for priming doses IVP).

Isotope rates of infusion:

- L-[ring-²H₅] phenylalanine: priming dose: 3.6µmol/kg. Constant infusion: 3.6 µmol/kg/hour.
- U-¹³C₉-¹⁵N-tyrosine: priming dose: 0.113µmol/kg. Constant infusion: 0.113µmol/kg/hour.
- L-[ring-²H₄] tyrosine: priming dose: 0.31µmol/kg.

IVP vials contain:	IVPB vials contain:

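### Section 3.1 allows a DEXA scan at Visit 1 without requiring the result of the pregnancy test collected at that same visit

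*Combined protocol and SAP*

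**What the plan says.** Section 3.1 makes consent the general condition for Visit 1 procedures: "Once consent is obtained, subsequent study procedures will be performed". On pregnancy it says: "Females of child bearing capacity will be asked to provide a urine sample for pregnancy testing". The samples then leave the site: "Blood and urine samples will be sent to LabCorp".

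The scan rule follows in the same description of Visit 1. If the subject has fasted for 8 hours, avoided caffeine for 12 hours and avoided strenuous exercise for 24 hours "to perform the DEXA scan and In Body scan on visit 1, these tests will be performed at that time". For subjects who do not meet those requirements, the rule is: "If they do not, these tests will be performed at Visit 2".

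Section 4.2 lists "Pregnant females" as an exclusion and does not say when the status must be established. Section 5.2 puts the DEXA dose at about half that of a chest x-ray, with one scan per subject, and does not mention pregnancy. Section 5.0 states: "There are no direct benefits for the subjects". The recruitment talking points in section 3.3 describe the schedule as "2 visits that are less than an hour, and 1 visit that lasts a bit over 10 hours".

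**The concern.** Pregnancy is an exclusion, and the test that would detect it is collected at the visit where the scan may take place. An exclusion protects a subject only if her status is known before the procedure that carries the risk. Section 3.1 gives its own list of conditions for scanning at Visit 1, words the result as a directive, and leaves pregnancy status off the list. A coordinator who follows the section literally could scan a woman at Visit 1 and learn afterwards that she should not have been enrolled.

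What is at stake is subject protection. The women concerned would receive a radiation dose in a study that offers them no direct benefit. No trial conclusion is at risk, because section 7.1 lists no body-composition outcome.

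**Working it through.** This is a question about the order of procedures. The protocol has no figure to reproduce, so the check sets the relevant sections side by side.

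1. **Earliest possible pregnancy sample.** Section 8.0 requires consent before any study procedure, and section 3.1 takes consent at Visit 1. The urine sample therefore cannot be collected before Visit 1.

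2. **Number and place of tests.** Section 3.1 names one pregnancy test across the three visits. No other urine sample appears in the protocol, so the urine sent to the outside laboratory must be this one. No on-site test is described.

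3. **Conditions for the scan at Visit 1.** Three are listed: fasting, caffeine and exercise. The number that concern pregnancy status is 0 of 3.

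4. **Time available.** Section 3.3 describes two visits of under an hour and one of just over 10 hours. Visit 3 is the 10-hour visit, so Visits 1 and 2 are the short ones. On that description, the time from urine sample to a Visit 1 scan is less than 60 minutes. A result would have to return from the laboratory within that time to be known before the scan. The protocol states no turnaround.

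5. **Any rule that puts the result first.** Sections 3.1, 3.3, 4.2, 5.2 and 8.0 were read for one, and none contains it.

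6. **Who could be affected.** Section 4.1 admits ages 18 to 40, section 3.6 stratifies by sex, and section 4.0 aims to balance the sexes within groups, with up to 28 subjects enrolled. Women who could be pregnant are thus an expected part of the sample.

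7. **Dose per affected woman.** 1 scan × ½ chest x-ray = about ½ chest x-ray.

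8. **Probability.** None is computed. It would need the number of women of child-bearing capacity, the share who arrive at Visit 1 fasted, caffeine-free and rested, the pregnancy rate, and the laboratory turnaround. The protocol gives none of these.

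Steps 1 to 3 and 5 establish the gap from the text alone. Step 4 bears on how likely the gap is to matter. Even with a fast result, section 3.1 does not tell staff to wait for it.

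**The case against.** The strongest reply is that section 4.2 excludes pregnant women at every visit, and that the three conditions in section 3.1 are preparation requirements for a valid scan and were never meant to restate eligibility. Section 3.1 also mentions the medical history, urine sample and blood draw before it mentions DEXA. On this reading, silence about pregnancy in the scan rule does not mean that scanning goes ahead regardless. That is a fair reading of the intent. But section 4.2 gives no timing, and it cannot protect a woman who is scanned before her result is known. Collecting a sample first is also not the same as having its result.

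A second reply is that the exposure pathway depends on an unstated turnaround, and that the under-an-hour figure comes from a plain-language recruitment talk, not from the visit schedule. Both points stand. The 60-minute limit is a recruitment estimate, and it may not allow for a Visit 1 that includes scans. The finding that no rule puts the result before the scan does not depend on either figure.

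Third, the consent form was not available for this review and may contain such a rule. That limit is accepted: the conclusion covers the protocol text only. Section 3.1 should still be complete in itself, since it is the instruction that directs the scan.

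Finally, the dose is low and the sample small, and this is an operational detail that does not touch the comparison of the groups. That is correct, and it is why the point is rated minor.

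**Conclusion.** The concern holds, as a minor subject-protection point limited to Visit 1. As written, section 3.1 permits a DEXA scan at the visit where the only pregnancy test is collected, and the protocol does not require the result first. By Visit 2 the result would probably be back and the exclusion in section 4.2 could then operate.

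The omission itself is certain within the protocol text. That a woman would actually be scanned with her status unknown rests on the assumption, likely but undocumented, that the laboratory result takes longer than the visit. The consequence is one exposure of about half a chest x-ray per affected woman, with a probability that cannot be quantified from the documents. No sample size, endpoint or analysis is affected.

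**What to change.** Add one condition to the Visit 1 scan rule in section 3.1: for females of child-bearing capacity, a negative pregnancy test result must be documented before DEXA. If the result is not available at Visit 1, do the scan in the Visit 2 slot that the protocol already provides, once the negative result is on file. An on-site urine strip read before the scan is an acceptable alternative and keeps the Visit 1 slot.

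The cost is one clause. Some women would have to fast for Visit 2 instead of Visit 1, or one inexpensive strip would be used per woman scanned at Visit 1. No visit is added, and no outcome in section 7.1 depends on when the DEXA is done.

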3.6 Randomization

Subjects will be stratified by sex and then randomized equally to one of three groups (one beef patty, one Impossible Burger, or two Impossible Burgers).

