7.0 Data Analysis

7.1 Statistical Analysis plan

The post-prandial change in net protein balance (i.e., protein synthesis minus protein breakdown) relative to the baseline in each group will be the primary outcome. Responses of the rates of protein synthesis and breakdown will be secondary outcomes. Additional secondary endpoints will be muscle protein synthesis, plasma EAA and insulin area under the curve above baseline values, and protein kinetics normalized by caloric and EAA intake. Correlation analysis of the relation between protein kinetics and the EAA content of the protein food source will be additional secondary endpoints.

One-way ANCOVA will be used to compare differences in protein kinetics (FSR, NB, PS, and PB) and protein kinetics normalized by caloric and EAA intake. Plasma EAAs and insulin area

under the curve above fasting values will be assessed by a one-way ANOVA. All significant main effects of group will be followed with Bonferroni-adjusted pairwise comparisons. Partial Pearson's correlation coefficients controlling for protein source (beef patty or Impossible Burger) will be used for the correlation analysis. Statistical significance will be accepted at $p < 0.05$.

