7.2 Sample Size Calculation & Power Analysis

A group size of 8 per group was a priori determined based upon an ANCOVA model to compare the protein sources and amounts with respect to mean response of net protein synthesis after adjusting for baseline measures. With this sample size, the ANCOVA model has 80% power to detect effect sizes of $f = 0.484$ or larger. This estimate assumes that the baseline covariate explains 50% of the variation in the response. A 5% α -level will be used to determine statistical significance.

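### The Visit 3 schedule has an undefined ingestion at 120 min, inside what the rest of the plan treats as a fasted baseline ending with the study food at 240 min

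*Combined protocol and SAP*

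**What the plan says.** The table in section 3.1 is the operational schedule for Visit 3; the text above it tells staff to take blood and muscle samples by it. Its 120-min row reads, after the blood draw, "ingest study supplement, muscle sample from vastus lateralis". Its 240-min row reads, again after the blood draw, "muscle sample from vastus lateralis serve study food".

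The Visit 3 text agrees with the 240-min row: "The study food is served after the 4:00 blood/muscle sample are obtained". Subjects arrive after an overnight fast.

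Elsewhere only burgers are described as the thing tested. Section 3.0 says "We will use a 10-hour period to measure the protein metabolism in response to the study food" and names one beef patty, one vegetarian burger or two. Section 3.6 randomizes to those three conditions, and section 5.3 lists them as the test foods. The only other mention of supplements is in section 4.2, which excludes people who cannot stop their own protein or amino acid supplements for 7 days before Visit 3.

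Section 7.3 describes an isotopic steady state in a fasted baseline period, then a 6-hour period after the patty. Section 7.1 defines the main endpoint as the post-prandial change in net protein balance "relative to the baseline in each group will be the primary outcome". Section 7.2 bases the sample size on an ANCOVA of "mean response of net protein synthesis after adjusting for baseline measures".

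**The concern.** The schedule contains an ingestion that the plan does not define, at a time that the rest of the plan treats as fasted. Two readings are possible, and each conflicts with other passages. As a separate item, it is a second intake 120 min before the study food, with no product, amount or composition given. As another name for the study food, it places the food at both 120 and 240 min. The document does not say which is meant.

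What is at stake is the baseline. It is subtracted to form the primary outcome, and it is the covariate in the ANCOVA. Section 7.3 takes fasted phenylalanine appearance as protein breakdown. It removes exogenous phenylalanine only for the test protein, and only in the post-prandial period. If something were eaten at 120 min, the baseline might be neither fasted nor at steady state, and the model has no term for that intake.

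The muscle endpoint is exposed in the same way, because the 120- and 240-min biopsies are the only pair that lies before food served at 240 min. There is also a disclosure gap: the allergy review in section 5.3 and the recruitment discussion in section 3.3 would not cover a separate item.

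**Working it through.** **Inputs.** From the section 3.1 table: blood draws at 0 and 120 min, then every 30 min from 150 to 600 min; biopsies at 120, 240 and 600 min. From the Visit 3 text: food after the 4:00 samples, that is 4 × 60 = 240 min, and an end at 10 h = 600 min. From section 7.3: a 6-hour post-prandial window.

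**Check on the table.** Draws: 2 (at 0 and 120 min) + 16 (150 to 600 min in steps of 30) = 18. At about 4 mL each, 18 × 4 = 72 mL, which is the total in section 5.1. The rows were therefore read completely.

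**The plan's own window.** 600 - 240 = 360 min = 6 h. This reproduces section 7.3. That section gives no clock time for the patty; 240 min is inferred from its 6 hours and the 10-hour total. The Visit 3 text and the 240-min row state the time directly.

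**The two times compared.**

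| | Ingestion at 240 min | Ingestion at 120 min |
|---|---|---|
| Time left to 600 min | 360 min (6 h) | 480 min (8 h) |
| Draws at or before that time | 6 (0, 120, 150, 180, 210, 240) | 2 (0, 120) |
| Draws after that time | 18 - 6 = 12 | 18 - 2 = 16 |
| 120-to-240-min biopsy interval | before ingestion | after ingestion |
| Agrees with the 6 h in section 7.3 | yes | no, 2 h longer |

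**What changes if the 120-min row is followed.** The draws after 120 and up to 240 min number 6 - 2 = 4 (150, 180, 210 and 240 min). These, the 240-min biopsy and the full 240 - 120 = 120 min between the first two biopsies would follow an ingestion. The 120-min draw and biopsy are not counted either way, because they share the row with the entry and their order is not otherwise stated. If the entry means the study food, no pair of biopsies lies wholly before ingestion.

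**What cannot be computed.** The composition of the item is not given, so no shift in phenylalanine appearance, net balance or muscle synthesis can be derived. The 72 mL blood total and the sample-size calculation do not depend on this point.

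**The case against.** The strongest reply is that the time of the study food is not in real doubt. The Visit 3 text and the 240-min row both state it, and the 6-hour window fits it. On that view, reading the entry as the food itself contradicts two explicit statements and one derived figure. Nor could staff give a separate item, since none is described. The entry then looks like stray wording in one row.

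Any harm is also doubly conditional: the row must have been followed, and the item must matter metabolically. The missing correction for exogenous phenylalanine, for example, bites only if the item supplies phenylalanine or protein. Finally, the hypotheses and the ANCOVA compare groups, and an item given identically at every subject's Visit 3 would affect all groups alike.

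Much of this stands. The entry may never have been acted on, and no effect on the primary outcome is shown. A common item would leave the between-group comparison less exposed than the within-group change. That relief would not apply if the entry meant the study food, because the food is what differs between groups.

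The reply does not remove the conflict. Calling the entry stray wording is a plausible guess that the document cannot confirm, and the entry sits in the table that staff are told to follow. The times in that table are labelled approximate, but that cannot bridge a gap of 120 min.

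**Conclusion.** The inconsistency is real and should be fixed. The 120-min entry is undefined and conflicts with the Visit 3 text, the 240-min row and the fasted baseline and 6-hour window of section 7.3. The conflict rests on the text alone.

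The consequence rests on one assumption, that the row was or would be followed. In that case 4 blood samples, one biopsy and a 120-min biopsy interval that belong to the baseline under the 240-min time would come after an ingestion. If the entry means the food, the post-prandial time would be 8 h instead of 6 h. The size and direction of any bias are unknown. No view is taken here on which entry is right.

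**What to change.** Reconcile the 120-min row with the 240-min row, the Visit 3 text and sections 3.0, 5.3 and 7.3, so that all describe the same ingestion event or events at the same time. Check that the baseline period in section 7.3 matches the reconciled time; its wording needs to change only if it does not. If any Visit 3 was run differently from the reconciled schedule, report how many in each group, so that a reader can judge whether the baselines are comparable.

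The cost is one table row, plus matching wording in section 7.3 if the reconciled time requires it.
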